3.0 Background Drug Information

MB is a phenothiazine derivative administrated intravenously for the treatment of drug-induced methemoglobinemia, currently its only labeled use. It has also been used topically as a photosensitizer for photodynamic therapy in the treatment of mucocutaneous lesions such as herpes labialis and oral lichen planus. In the laboratory setting it is utilized as an indicator dye, and in cancer treatment, it is used for preoperative planning for breast cancer patients undergoing lymph node biopsy. Although the exact mechanism of action of MB has not been established, it is known to metabolize to a colorless form, leukomethylene blue, forming a reversible oxidation-reduction system, which explains its utility in methemoglobinemia. It is also known to be neurolytic when injected intradermally (11), and as a result of this observation, it has been used intradiscally for the treatment of discogenic pain (8) and into pelvic fracture sites for associated pain (13). These properties may help explain the anti-

inflammatory and analgesic effects of MB, leading to its proposed clinical utility in painful oral mucositis.

3.1 Dosages and Administration

For oral administration, no commercially available preparation exist, but it has been prepared by diluting MB 1%, 5-10 mL of commercially available 10mg/mL solution with 100-200 mL of water (9, 14). Based on our anecdotal experience, at MD Anderson same dilution has been used in more than 80 patients with pain associated to oral mucositis with no adverse events.

Patients be instructed to take one mouth full (6 – 10 mL of the solution to be held at the painful sites for five minutes then to swish and spit. The same steps to be repeated every 6 hours (the total mix of 100 mL will provide up to 6-10 uses).

3.2 Adverse Effects, Precautions, and Contraindications

If used systemically, MB administered intravenously (IV) or orally (PO) in large doses may cause nausea, vomiting, abdominal pain, dizziness, headache, profuse sweating, dyspnea, mental confusion, and irritation at the infusion site (only seen with IV). The most common side effects of oral administration are adverse gastrointestinal effects and dysuria. MB causes a blue-green discoloration to saliva, urine, feces, and skin. The skin stains may be removed by application of hypochlorite solution. MB is contraindicated in patients with known hypersensitivity to MB, women who are or may become pregnant (MB is a teratogen), patients with known or suspected glucose-6-phosphate dehydrogenase (G6PD) deficiency, and those who are taking serotonergic drugs. It should be used cautiously in patients with severe renal impairment. Subcutaneous, intrathecal, and intraspinal route of administration should be avoided. Long-term use of MB is also associated with anemia. Therefore, monitoring of complete blood counts is advised (15). These adverse events have been studied in both large IV and PO administration and appear to be much more limited with oral administration (as above). In our study, the use of 100 mL equals 4 - 6 mouth full doses. It might expose patients to a dose of 2-6 mg of MB if swallowed, trans-mucosal absorption if any, when used in an oral rinse, is considered negligible. Formal toxicity monitoring may not be required. Therefore, formal toxicity monitoring will not be necessary. Safety data will be monitored by principle investigator.

If not available, a pregnancy test will be done in females in child-bearing condition (non-menopausal). This study requires women of child bearing potential to use contraception or abstinence from sex during the treatment period and for 30 days after their last dose. Urine pregnancy test will be obtained within 48 hours of staring the study.

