3.4 Preparations, Stability, and Storage

MB is a thiazine dye that is soluble in water and forms a deep blue solution. It is available as a 1%, 10 mg/mL solution that should be stored at 20°C to 25°C (68°F to 77°F) but may be exposed to temperatures ranging from 15°C to 30°C (59°F to 86°F).

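### The 2-6 mg swallowed exposure in section 3.2 has no stated basis or arm and does not follow from the protocol's own figures; uses per 100 mL and rinse frequency also conflict across sections 3.1, 3.2 and 6.4

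*Combined protocol and SAP*

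**What the plan says.** Section 4.0 sets three methylene blue (MB) arms, at 0.025%, 0.05% and 0.1%. Section 3.4 fixes the unit conversion: "It is available as a 1%, 10 mg/mL solution".

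On volume, section 3.1 describes a mouthful as "6 – 10 mL of the solution to be held at the painful sites", and section 6.4 repeats 6-10 mL per rinse. On frequency and supply, section 3.1 says: "The same steps to be repeated every 6 hours (the total mix of 100 mL will provide up to 6-10 uses". Section 6.4 repeats both figures, tells patients to continue until pain resolves or the 100 mL is used up, says 100 mL might last 2-3 days, and then concludes that there are three rinses a day, 6 hours apart.

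Section 3.2 gives a different count: "In our study, the use of 100 mL equals 4 - 6 mouth full doses". It continues: "It might expose patients to a dose of 2-6 mg of MB if swallowed", and adds that "trans-mucosal absorption if any, when used in an oral rinse, is considered negligible". It then says that formal monitoring may not be needed and ends: "Therefore, formal toxicity monitoring will not be necessary".

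**The concern.** The exposure figure cannot be interpreted as it stands, because a milligram amount means something different per mouthful, per day and per bottle, and the three arms differ fourfold in concentration. On the most natural reading, one swallowed mouthful, it is too low for the 0.1% arm.

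This matters because of where the figure stands. It is the only quantitative exposure in section 3.2 ahead of the statement on toxicity monitoring. The remark on negligible absorption concerns uptake through the mucosa, so it does not cover rinse that is swallowed. A medical monitor or ethics committee reading section 3.2 would take 6 mg as the ceiling.

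The conflicts over uses and frequency lie in the operative instructions. Treatment can end when the 100 mL is used up, so the number of uses per 100 mL and the rinses per day together set how long it can last. Section 8.1 has staff collect adherence to the medication schedule, and the documents give two schedules.

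**Working it through.** **Inputs.** 1% = 10 mg/mL (3.4); arms 0.025%, 0.05% and 0.1% (4.0); 6-10 mL per rinse (3.1, 6.4); 4-6 mouthfuls per 100 mL (3.2); up to 6-10 uses per 100 mL (3.1, 6.4); every 6 hours (3.1, 6.4); three rinses per day (6.4).

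**Concentrations.** Percent × 10 mg/mL gives 0.25, 0.5 and 1 mg/mL. The recipe in section 3.1, "5-10 mL of commercially available 10mg/mL solution with 100-200 mL of water", agrees: 5-10 mL × 10 mg/mL = 50-100 mg; made up to 100-200 mL this runs from 50/200 = 0.25 to 100/100 = 1 mg/mL. If the water is added on top, it runs from 50/205 = 0.24 to 100/110 = 0.91 mg/mL.

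**Trying to reproduce 2-6 mg.** Swallowed amount = concentration × volume, with the whole volume swallowed:

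| Reading | 0.025% (mg) | 0.05% (mg) | 0.1% (mg) |
|---|---|---|---|
| One rinse, 6-10 mL (3.1, 6.4) | 1.5-2.5 | 3-5 | 6-10 |
| One rinse, 100 mL over 6-10 uses = 10-16.7 mL (3.1, 6.4) | 2.5-4.2 | 5-8.3 | 10-16.7 |
| One rinse, 100 mL over 4-6 mouthfuls = 16.7-25 mL (3.2) | 4.2-6.3 | 8.3-12.5 | 16.7-25 |
| One day, 3 rinses of 6-10 mL | 4.5-7.5 | 9-15 | 18-30 |
| One day, 4 rinses of 6-10 mL | 6-10 | 12-20 | 24-40 |
| Whole 100 mL | 25 | 50 | 100 |

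No row gives 2-6 mg across the arms. The closest match is a fixed 6 mL in every arm: 6 × 0.25 = 1.5, 6 × 0.5 = 3 and 6 × 1 = 6 mg. That uses only the bottom of the stated volume range. At 6-10 mL the 0.1% arm starts at 6 mg and exceeds it by up to 10 − 6 = 4 mg. The daily and bottle rows are upper bounds, because the rinse is meant to be spat out.

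**Uses per 100 mL.** At 6-10 mL per rinse, 100/10 = 10 to 100/6 = 16.7 uses. Section 3.2 says 4-6; sections 3.1 and 6.4 say up to 6-10. The implied count meets the second only at 10 mL and 10 uses, and does not meet the first at all: 4-6 mouthfuls of 6-10 mL use between 4 × 6 = 24 mL and 6 × 10 = 60 mL.

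**Frequency.** Every 6 hours is 24/6 = 4 rinses per 24 hours, against three in the conclusion of section 6.4. Three rinses 6 hours apart span 2 × 6 = 12 hours and leave a 12-hour gap.

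**Duration of 100 mL** = uses / rinses per day:

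| Uses | At 4 per day | At 3 per day |
|---|---|---|
| 4-6 | 1-1.5 days | 1.3-2 days |
| 6-10 | 1.5-2.5 days | 2-3.3 days |
| 10-16.7 | 2.5-4.2 days | 3.3-5.6 days |

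The stated 2-3 days fits best with 6-10 uses at three per day, which is neither the count in section 3.2 nor the 6-hourly instruction.

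**The case against.** The strongest reply is that the sentence is hedged and describes a rinse that is spat out, so the figure may allow for partial swallowing, or may be a rounded result for a 6 mL mouthful. Section 6.4 also says that strict precision is not needed. This stands to a degree: the defect certain from the text is the missing basis, and the size of any understatement depends on the reading. But no swallowed fraction is stated. To stay within 6 mg, a patient in the 0.1% arm could swallow at most 6/10 = 60% of a 10 mL rinse, and nothing in the documents says so.

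A second reply is that practical impact is limited. Adverse events are assessed on set days to Day 30 (6.5), toxicity is collected weekly (8.1), and safety summaries go to the medical monitor after every 5 evaluable patients per arm (7.3). Section 3.2 also offers other grounds: negligible mucosal absorption and more limited effects with oral use. All of this stands. The link between the figure and the monitoring statement is inferred from their position; the text does not state it.

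On frequency, the two statements agree if an overnight rinse is skipped. That is plausible, but the protocol does not say it.

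A reader might also infer that the conflict over frequency biases the results, since a patient taking three rinses would be fully adherent on one schedule and 3/4 = 75% on the other. The documents do not support this. Section 7.3 measures compliance by comparing dropout rates, section 7.2 defines the per-protocol set by completion of the allocated treatment without a rinse count, and no percent-adherence measure is defined.

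**Conclusion.** The point holds as an inconsistency in the documents. The 2-6 mg figure has no stated basis or arm, and no full-swallow reading of the stated ranges reproduces it. Per rinse at 6-10 mL, its maximum is the minimum for the 0.1% arm (6-10 mg). On section 3.2's own mouthful count, all three arms can exceed 6 mg, so the problem should not be described as confined to the 0.1% arm. These sizes assume that the whole rinse is swallowed. Uses per 100 mL and rinse frequency conflict whatever is assumed about swallowing.

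Three stronger conclusions are not supported:

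- A reader might infer that the decision on toxicity monitoring is wrong. The documents give no toxicity threshold, and adverse events are still collected, so the corrected figure may or may not alter it.
- A reader might take the roughly 80 earlier patients without adverse events as a ground for that decision. They appear in sections 1.0 and 3.1, and section 3.2 does not cite them.
- A reader might infer that an endpoint or analysis set is affected. The planned schedule is ambiguous for the adherence collected under section 8.1, but no planned analysis is shown to change.

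**What to change.** The sponsor should reconcile rinse volume, uses per 100 mL and rinse frequency across sections 3.1, 3.2 and 6.4, including the two statements within section 6.4. The swallowed exposure should then be recomputed by arm from the reconciled figures, with its basis stated (per rinse, per day or per 100 mL, and any assumed swallowed fraction), and should replace 2-6 mg in section 3.2. The medical monitor should confirm the monitoring statement against the corrected exposure. Which volume, dose, schedule or monitoring rule applies is for the sponsor to settle; none is proposed here.

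The cost is minor rewording and one review by the medical monitor. The downside is that the stated exposure is likely to look less favourable.

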3.3 Drug Interactions

MB is an inhibitor of monoamine oxidase (MAO), in full doses; serious central nervous system reactions (serotonin syndrome) have been reported with patients who are concurrently taking serotonin-modulating medications (16). Discontinuing the serotonergic medication prior to administration of MB can reduce the risk of serotonin syndrome. If given systemically, the Food and Drug Administration (FDA) recommends most serotonergic drugs to be discontinued for at least two weeks prior to MB treatment in non-emergency situations

(16). Most of the reported cases of serotonin syndrome occurred when MB was used as a diagnostic agent in the operative setting, in patients taking selective serotonin reuptake inhibitors (SSRI) or selective serotonin-norepinephrine reuptake inhibitors (SNRI). Other drug interactions are similar to those with other drugs having MAO-inhibiting properties, e.g., anticholinergics, alpha/beta-agonists, and tricyclic anti-depressants (15). These interactions have been studied in the IV route of administration and are likely more limited with oral administration of small dosages as proposed in this study.

3.4 Preparations, Stability, and Storage

MB is a thiazine dye that is soluble in water and forms a deep blue solution. It is available as a 1%, 10 mg/mL solution that should be stored at 20°C to 25°C (68°F to 77°F) but may be exposed to temperatures ranging from 15°C to 30°C (59°F to 86°F).

4.0 Study Design

This study is a prospective, randomized trial involving adult patients with intractable pain associated with oral mucositis. This study will have four intervention arms - MB 0.025 arm, MB 0.05 arm, MB 0.1 arm and a control arm. MB arm will receive one of 0.025%, 0.05% or 0.1% MB solution in addition to conventional therapy (0.025%, 0.05%, and 0.1% MB solution for MB 0.025, MB 0.05, and MB 0.1 arm, respectively), and the control arm will receive conventional therapy for 2 days, then will receive one of 3 solutions which will be randomly selected if they would like to receive MB solution.

5.0 Study Population

Patients will be randomized as described below. Neither the physician nor the patient will be involved in the randomization process. Physician, patient, study coordinator and data collectors will be blinded to the concentration of the medication used.

5.1 Sample Size

For the primary outcome (Oral mucositis pain reduction from baseline to 7 days after entering the study), we expect the mean pain reduction of 0, 2, 2.5, and 3 points for control, MB 0.025, MB 0.05, and MB 0.1 arms, respectively. In a one-way ANOVA study, sample sizes of 15, 15, 15, and 15 are obtained from the 4 arms whose means are to be compared. The total sample of 60 subjects achieves 83% power to detect differences among the means versus the alternative of equal means using an F test with a 0.05 significance level. The size of the variation in the means is represented by their standard deviation which is 1.14 (means of 0, 2, 2.5, and 3 for control, MB 0.025, MB 0.05, and MB 0.1 arms, respectively). The common standard deviation within a group is assumed to be 2.5.

5.2 Inclusion Criteria

1. Patients with a cancer diagnosis, receiving chemotherapy, radiation therapy or the combination.
2. Patients with a current diagnosis of oral mucositis.
3. Patients with pain and oral dysfunction associated with oral mucositis despite conventional therapy.
4. Age greater than or equal to 18 years.
5. Voluntary written consent.
6. Patient must agree to use of contraception or abstinence from sex during the treatment period and for 30 days after patients' last dose of study MB.

5.3 Exclusion Criteria

1. Patients with known allergy to MB.
2. Patients taking medications with known significant drug interactions.
3. Pregnant or lactating patients.
4. Patients who are cognitively impaired and unable to consent for the study.
5. Patients with risk of Broncho-aspiration based on documented swallowing test by a Speech Pathologist (if available).
6. Patients with known history of G6PD deficiency.
7. Patients undergoing any other experimental intervention for oral mucositis.
8. Patients who have no pain or impairment in oral function, patients who are not symptomatic.
9. Patients with head and neck cancer.
10. Patients on serotonergic drugs.

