6.3 Patient randomization and assignment to treatment arm

The study will accrue up to 60 patients with a 1:1:1:1 ratio to include 4 intervention arms. Those include conventional therapy, conventional therapy + MB 0.025%, conventional therapy + MB 0.05%, and conventional therapy + MB 0.1%; each group will include 15 patients. We will conduct stratified randomization by baseline pain (baseline NRS 0-5 vs. 6-10) and oral functioning score (0-3 vs. 4-6). The primary endpoint is the reduction in pain score from baseline to 7 days. Patient randomization will be done through the Clinical Trial Conduct website. Study staff will be uninvolved in the randomization process.

Once a patient is enrolled in the study, the Investigational Pharmacy at MDACC retrieves the randomized treatment arm information from the Clinical Trial Conduct website. Once a patient is randomized to a treatment arm, Investigational Pharmacy will relay the information to the dispensing pharmacy at MDACC.

Study staff will contact patients either in person if as an inpatient or by phone at every follow-up the encounter to check for adverse events during routine patient encounters or via telephone calls.

Patients who were randomized to conventional arm will have an option to cross over to one of 3 MB arms, which they will be randomly allocated to, after completing 2 day pain measurements.

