6.4 Administration of pharmacological agent

Preparation and randomization of the study medication (MB) for each patient will be performed by a compound research pharmacy. The study medication will be available to the patient through the dispensing pharmacy at MD Anderson Cancer Center. Patients will receive instructions on how to take study medications.

The participants will take MB via oral swish and spit technique or to continue conventional therapy. A small cup will be given to the patient to use to take the MB. There is no need for strict precision of the MB because patients' mouth size are variable, usually takes 6-10mL per rinse. Those on the MB arm will be instructed to take one mouth full (6 – 10 mL out of a total of 100 mL which might last 2-3 days only if used regularly) of the solution to be held at the painful sites for five minutes then to swish and spit. The same steps to be repeated every 6 hours (the total mix of 100 mL will provide up to 6-10 uses). If needed, patients will be given the solution to complete the treatment at home. Patients are instructed to use it every 6 hours until pain resolves or the total 100 mL of the mix are used. Therefore, the MB rinse is 3 total rinses per day, 6 hours apart.

Unused MB will be returned to Investigational Pharmacy Services at MDACC by the study staff for future incineration in accordance with the current SOP.

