6.5 Data collection

Patients enrolled in the study will be asked to complete a baseline assessment questionnaire in person, including the Modified Harris mucositis-related pain assessment tool. The patient will have subsequent follow-up interviews at 1, 2, 7 days with repeat assessment of the Modified Harris mucositis-related pain assessment tool. Furthermore, on Baseline, Day 0, Day 1, Day 2, Day 7 and Day 30, adverse event will be assessed, and this maybe by telephone or face-to-face in the clinic. The patient's medication use will also be assessed at follow-up, including morphine equivalent daily dose (MEDD) and other reported analgesics used for the treatment of their mucositis-related pain. Lastly, the research team will investigate if any patient reported any side effects from the treatment.

All completed data will be stored electronically in the MD Anderson REDCap system, in a locked file, on password-protected computers. Only research team members will access the files. Subject registration will be entered into CORe database.

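### Exclusion 6 bars only known G6PD deficiency, although Section 3.2 also contraindicates methylene blue when deficiency is suspected

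*Combined protocol and SAP*

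**What the plan says.** Section 3.2, part of the background drug information, states that MB is contraindicated in four groups: people with known hypersensitivity to it; women who are pregnant or could become so; "patients with known or suspected glucose-6-phosphate dehydrogenase (G6PD) deficiency"; and people on serotonergic drugs. The sentence is not restricted to a route or dose.

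The same section then plays down exposure from the study product: "trans-mucosal absorption if any, when used in an oral rinse, is considered negligible". It concludes that formal toxicity monitoring is unnecessary.

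Section 5.3 holds the exclusions. Number 6 reads "Patients with known history of G6PD deficiency". Number 3 reads "Pregnant or lactating patients" and number 10 reads "Patients on serotonergic drugs".

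Section 6.4 describes one 100 mL mix "which might last 2-3 days only if used regularly". On follow-up, Section 6.5 states that "on Baseline, Day 0, Day 1, Day 2, Day 7 and Day 30, adverse event will be assessed", by telephone or face to face.

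**The concern.** A contraindication and the exclusion that implements it should cover the same patients unless the protocol explains the difference. Here the background section names two groups, known and suspected deficiency, and the eligibility list names one. Staff who screen against the numbered list in Section 5.3 could correctly enrol a patient with suspected but undiagnosed deficiency, and that patient would then receive a drug that Section 3.2 says is contraindicated.

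What is at stake is the safety of an individual patient and the internal consistency of the protocol. Recruitment runs through the emergency center, the pain clinic and the oncology wards (Section 6.1), so several teams may be applying the list.

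**Working it through.** The protocol attaches no figure to this point, so the check is mainly a comparison of texts.

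**Step 1. Each contraindication in Section 3.2 against its eligibility rule.**

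- Hypersensitivity: 3.2 says known; exclusion 1 says known allergy. Same scope.
- Serotonergic drugs: 3.2 names current users; exclusion 10 names current users. Same scope.
- Pregnancy: 3.2 covers pregnant women and those who could become pregnant. Exclusion 3 bars pregnant or lactating patients. Women who could become pregnant are admitted with contraception or abstinence (inclusion 6) and a urine test within 48 hours of starting (Section 3.2). The scope is adapted, with a stated substitute safeguard.
- G6PD deficiency: 3.2 covers known and suspected; exclusion 6 covers known history. The suspected group has no rule and no substitute safeguard.

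**Step 2. Does anything else catch suspected deficiency?** Inclusions 1-6 do not mention it. Exclusion 2 concerns interacting medications, and an enzyme deficiency is not a medication. The remaining exclusions concern cognition, aspiration risk, other experimental treatment, absence of symptoms, and head and neck cancer. There is no catch-all or discretion clause. The only eligibility-related laboratory test is for pregnancy. Blood counts are advised in Section 3.2 in connection with long-term use, but none is scheduled.

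**Step 3. Do later checks fill the gap?** Adverse events are assessed at baseline and on Days 0, 1, 2, 7 and 30 (Section 6.5). Toxicity is collected weekly (Section 8.1). A summary goes to the Medical Monitor after every 5 evaluable patients per arm (Section 7.3), which at 15 per arm means reports at 5, 10 and 15. All of these can detect harm, but none screens for G6PD deficiency before dosing.

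**Step 4. How many patients does exclusion 6 govern?** Section 6.3 says "each group will include 15 patients". Three MB arms give 3 × 15 = 45 of 60, or 75%, randomised to MB. Up to 15 controls may opt for it after the Day 2 measurements. These are counts of patients who may receive MB. They do not count patients with suspected deficiency, for which the documents give no figure.

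**Step 5. Dose in one mouthful.** Section 3.4 equates 1% with 10 mg/mL, so 0.025% is 0.25 mg/mL and 0.1% is 1 mg/mL. With 6-10 mL per rinse (Section 6.4):

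- lowest: 0.25 mg/mL × 6 mL = 1.5 mg
- highest: 1 mg/mL × 10 mL = 10 mg

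Section 3.2 gives 2-6 mg if swallowed. Intended use is to spit, so the absorbed amount should be well below either range.

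**Step 6. Effect on the design figures.** The stated 83% power reproduces. The noncentrality is 15 × 5.1875 / 2.5² = 12.45, where 5.1875 is the sum of squared deviations of the means 0, 2, 2.5 and 3 about 1.875. With 3 and 56 degrees of freedom and a critical F of 2.769, power is 82.7%. Exclusion 6 enters none of these inputs.

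**The case against.** The strongest defence is that Section 3.2 describes the drug in general. It opens with large intravenous or oral doses and says adverse effects appear much more limited with oral administration. The study product is spat out, and about 80 earlier patients had no observed adverse event (Section 1.0). A narrower G6PD criterion is compatible with that reasoning. Also, pregnancy and medication use can be checked objectively, whereas the documents never define a suspected deficiency, and exclusion 1 likewise uses known. A preference for a criterion that can be ascertained is a plausible explanation.

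This lowers the weight of the point but does not remove it. The contraindication sentence is not limited to systemic use. The protocol never cites low absorption, or difficulty of ascertainment, as a reason to relax the G6PD rule. For hypersensitivity, Section 3.2 itself says only known, so exclusion 1 is no precedent for dropping the suspected group. The G6PD status of the earlier patients is not given.

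Two stronger readings are tempting and should be resisted.

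- A reader might infer that G6PD deficiency is the only contraindication changed on its way into Section 5.3. It is not: the one for women who could become pregnant is also adapted. The caution in severe renal impairment, a precaution and not a contraindication, has no criterion either. Departure from the wording of Section 3.2 is therefore not proof of an oversight.
- A reader might infer that eligibility is the only place where the contraindication can operate before dosing. Section 3.2 belongs to the same protocol and warns any investigator who reads it. The fault is an inconsistency between two sections; the warning itself is present.

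**Conclusion.** The point holds as a minor safety-wording correction. Section 3.2 contraindicates MB in suspected as well as known G6PD deficiency, exclusion 6 bars only the known cases, and nothing else in the protocol covers the rest. No reason is given for the difference.

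The practical risk is probably small. That judgement assumes that patients spit the rinse out, that absorption is as low as Section 3.2 says (a statement made there without a citation), and that use lasts about 2-3 days. The number of affected patients is unknown. The 45 patients randomised to MB, or all 60 if every control opts in, should not be read as patients at risk from this gap.

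There is no consequence for power, the primary analysis or the interpretation of the pain outcome.

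**What to change.** Reword exclusion 6 in Section 5.3 to: *Patients with known or suspected G6PD deficiency*. The sponsor may add *unless an available G6PD result excludes it*, so that a patient already tested is not lost needlessly. The documents do not say what should count as suspicion. If sites want guidance, the sponsor should supply a short definition.

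No mandatory assay is needed to align the two sections. Controls who later opt for MB have met the same criterion before randomisation, so no second check at crossover is required.

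The cost is a one-line amendment and possibly a few extra screen failures. Sample size, visit schedule and analysis stay as they are.

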5.5 Conventional Therapy Criteria

The conventional therapy includes oral rinses and systemic therapy (oral, transdermal and intravenous analgesic. No response to conventional therapy means using other treatments and still symptomatic.

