6.0 Methods

6.1 Patient enrollment and registration

Patients will be recruited for the study through multiple care sites at MD Anderson Cancer Center. Patients arriving at the MDACC Emergency Center with complaints consistent with mucositis will be screened for eligibility for enrollment in the study. Other patients treated at

the Pain Management Center as well as those referred for mucositis treatment from the Oncology medical wards for mucositis will also be screened.

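### No eligibility criterion covers earlier methylene blue (MB) rinse, although the site already gives it, so patients who have used or failed it in the current episode can be randomised

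*Combined protocol and SAP*

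**What the plan says.** Section 1.0 (Background and Rationale) reports that the site's consulting service has given MB rinse at 0.025%, 0.05% or 0.1% to about 80 patients with intractable mucositis pain. They were seen as inpatients, in the Emergency Department and in outpatient clinics. Section 3.1 says of the site that the "same dilution has been used in more than 80 patients".

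Section 6.1 recruits from the Emergency Center and also screens patients of "the Pain Management Center as well as those referred for mucositis treatment" from the oncology wards.

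Section 5.3 has ten exclusions. Exclusion 1 is MB allergy. Exclusion 7 is "Patients undergoing any other experimental intervention for oral mucositis". None mentions earlier MB rinse, and no washout is given.

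Section 5.5 says that conventional therapy includes oral rinses, without listing them, and adds: "No response to conventional therapy means using other treatments and still symptomatic". Section 1.0 is narrower: anaesthetic and cleaning rinses plus systemic analgesics. Sections 2.0 and 4.0 define the MB arms as MB added to conventional therapy.

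Section 6.5 collects morphine-equivalent dose and other analgesics at follow-up. It names no item for MB rinse taken before or outside the trial.

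**The concern.** The trial tests a treatment that its own site has been giving, at the same concentrations, to the same kind of patient. In that setting one expects a rule on previous exposure, and there is none. Exclusion 7 applies to a patient who is undergoing something else now. It does not apply to one who stopped MB rinse last week because it did not help.

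Such a patient can meet the entry conditions. Inclusion 3 asks for pain and oral dysfunction despite conventional therapy, and the Background says that all the patients treated so far had suboptimal control despite systemic opiates. Someone who then failed MB as well is still symptomatic and still qualifies.

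Randomisation would spread such patients over the four arms on average, so the expected effect is a smaller average benefit in the MB arms rather than systematic imbalance. With 15 per arm, one or two patients are 7–13% of an arm (1/15 and 2/15), and previous MB use is not a stratification factor, so chance imbalance is also possible. Without a recorded exposure, the analyst cannot reliably find these patients or run a sensitivity analysis without them.

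**Working it through.** **Inputs (Section 5.1, repeated in 7.1; allocation in 6.3).** Mean reductions: "we expect the mean pain reduction of 0, 2, 2.5, and 3 points for control, MB 0.025, MB 0.05, and MB 0.1 arms". Within-group SD 2.5, n = 15 per arm, test level "using an F test with a 0.05 significance level".

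**Step 1: reproduce the plan's power.** The grand mean is (0 + 2 + 2.5 + 3)/4 = 1.875. The squared deviations sum to 3.5156 + 0.0156 + 0.3906 + 1.2656 = 5.1875. The SD of the means is √(5.1875/4) = 1.139, against 1.14 in the plan. The non-centrality is λ = n·Σ(μᵢ − μ̄)²/SD² = 15 × 5.1875/6.25 = 12.45, with 3 and 56 degrees of freedom and critical F = 2.77. Power is 82.7%. The plan says: "The total sample of 60 subjects achieves 83% power to detect differences among the means". The figure is correct.

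**Step 2: previous MB failures in the MB arms.** Let a share g of each MB arm gain nothing from MB. The MB means become (1 − g) × (2, 2.5, 3), the control mean stays at 0, and λ = 12.45 × (1 − g)². The documents give no value for g; those below are assumptions. The first power column holds the SD at 2.5. The second simulates individual patients, so mixing those who gain with those who do not also widens the spread within an arm.

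| g (assumed) | λ | Power, SD fixed | Power, simulated |
|---|---|---|---|
| 0% | 12.45 | 83% | 83% |
| 10% | 10.08 | 73% | 70% |
| 20% | 7.97 | 62% | 57% |
| 30% | 6.10 | 49% | 44% |

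With the SD fixed, about 19 per arm would restore roughly 83% at g = 10%, and about 23 per arm at g = 20%.

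**Step 3: limits of this calculation.** Gaining nothing is the worst case for an earlier user. One who responded before might respond again, and the contrast could then move the other way. The table shows how sensitive 15 per arm is; it is not an estimate of loss.

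**Step 4: current use and the comparator.**

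- *Exclusion 7 beside Sections 3.0 and 3.1.* MB's only labelled use is intravenous, for methaemoglobinaemia, and no commercial oral preparation exists. A compounded MB rinse taken outside the trial can reasonably be read as another experimental intervention, so current users are probably barred.
- *Section 5.5 beside Sections 1.0, 2.0 and 4.0.* Section 5.5 leaves oral rinses unspecified, while the other three describe conventional therapy without MB or set MB on top of it. Read together, MB is not conventional therapy, but the section that formally defines the comparator does not say so.

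**The case against.** The strongest reply is that no exposed pool has been shown. The roughly 80 patients are described largely in the past tense, over an unstated period, and nothing says that non-study use continues during recruitment. The Background also describes chemotherapy mucositis as resolving within about two weeks, so most past cases would not be in a current episode. It adds that the majority had a sustained fall of more than half in their pain scores, so failures were a minority. All of this bears on frequency and stands: the frequency is unknown and may be low. It does not close the gap for a patient who received the rinse earlier in the same episode.

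Two stronger readings are tempting, and the documents do not support them. A reader might infer that Exclusion 7 lets current users of the site's rinse into the trial; step 4 shows why it more plausibly bars them, although screeners could differ. A reader might also infer from Section 5.5 that controls may use MB as conventional therapy. The Background's description and the definition of the arms contradict that. The open wording is a drafting gap, not permission.

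It can also be said that a baseline score lowered by MB would bias the comparison. Randomisation is stratified by baseline NRS and oral function (Section 6.3), so this would not by itself produce bias, though it may leave less room to improve.

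Finally, the Day 2 cross-over in Section 6.3, with crossed-over controls counted in the MB arm under Section 7.2, is a larger and documented threat to the Day 7 comparison. That is true and separate. It does nothing about previous MB failures randomised to the MB arms.

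**Conclusion.** The point holds in a limited form. Earlier MB rinse in the current episode is not covered by any criterion or washout, and no named data item records it, at a site known to have given it. Such patients can be randomised, and the omission could not be reliably repaired at analysis. The consequence is possible dilution or distortion of the contrast, in a direction that is likely but not certain.

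The size is conditional. A 10% share with no benefit would cost about 9 to 13 points of power (82.7% to 73.2% with the SD fixed, or to about 70% by simulation), taking the plan's means and SD as true. The share itself is an assumption. The sample-size calculation contains no error. This is a cheap improvement worth making, not a flaw that invalidates the design.

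**What to change.** - **Section 5.3:** reword Exclusion 7 so that it also covers previous or current MB oral rinse outside the trial for the current mucositis episode.
- **Section 5.5:** state that non-study MB rinse is not part of the conventional-therapy comparator, in line with Section 1.0.
- **Section 6.5:** record any non-study MB rinse at baseline and at Days 1, 2 and 7. The follow-up items could be added to the medication questions already planned; the baseline item is new.

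The cost is one eligibility line, one sentence and one data field, plus a slightly smaller eligible pool at a site that has been using MB. None of this resolves the Day 2 cross-over, which needs its own correction.
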